Rationale:	
Chronic rhinosinusitis (CRS) is an inflammation of the nose and paranasal sinuses and is characterized by two or more symptoms, one of which should be either nasal blockage/obstruction/congestion or nasal discharge (anterior/posterior nasal drip), lasting for 12 weeks or longer. In addition, facial pain or pressure and a reduction in the sense of smell can occur [1]. The condition can occur with or without nasal polyps.
 
Chronic rhinosinusitis (CRS) is a significant health problem and affects 5-12% of the general population [1].
 
The physiopathology of CRS is poorly understood with multiple environmental, host and microbial factors being implicated. Putative pathological factors include changes in the microbiota, imbalance of the local or systemic immune system, allergens, toxins and genetic predisposition [2].
 
A dysbiosis mechanism has been proposed as modulating inflammation in diseased sinuses. This hypothesis suggests that externally influenced changes in the nasal microbiome can result in dysbiosis, i.e. a shift from a “normal” or “healthy” microbial community structure and that this shift may be responsible for the initiation or maintenance of CRS. For example, the disruption of the commensal biofilm during a viral upper respiratory tract infection can create a niche for pathogenic species to grow [3]. Despite many contradictory statements in the different studies some common trends emerge. Less diversity in the microbial community rather than an increased overall bacterial load seems to characterize CRS compared to the healthy state with no consensus about specific genera indicative of disease [4], [5], [6]. However, anaerobes and S. aureus are found to be significantly more

	
prevalent and abundant in CRS versus healthy controls [4]. Bacterial biofilm is detected on the sinus mucosa in up to 80% of CRS patients and its presence does not imply that it is causing mucosal inflammation. However, in the context of CRS, there are several possible mechanisms by which biofilms may be pro-inflammatory including the release of planktonic organisms and the release of superantigens, which can cause ciliary dysfunction and inhibition of ciliary clearance. Bacterial biofilms are likely a key modulator of the refractory nature of CRS [7].
 
Although clinical evidence from well-designed trials is scarce, European Guidelines for chronic rhinosinusitis recommend daily nasal saline irrigation for reduction of the severity of symptoms of CRS [1]. A recent Cochrane analysis has concluded that daily nasal irrigation with hypertonic saline solution is more effective than placebo to improve patient symptoms [8]. The exact mechanisms by which nasal irrigation works are not known. However, most of the experts agree that it is primarily a mechanical intervention leading to direct cleansing of the nasal mucosa. Nevertheless, the efficacy of such solution remains moderate.
 
Healsea® Chronic is a CE marked medical device indicated in adults for the treatment of nasal symptoms of chronic rhinosinusitis. This is a seawater-based nasal spray supplemented with a natural Symbiofilm® extract (0.02%) isolated from marine bacteria. The nasal solution is hypertonic (NaCl 2.2%). Symbiofilm® is a marine postbiotic comprising active exopolysaccharides with emulsifying properties and in vitro antibiofilm activity. Antibiofilm properties have been demonstrated with the colorimetric microtiter plate assay [9]. In this model, a significant inhibition of biofilm formation by Staphylococcus aureus and Haemophilus influenzae are observed. Detachment properties from human nasal epithelial cells of Staphylococcus aureus and Pseudomonas aeruginosa has also been demonstrated in vitro, suggesting an inhibition of biofilm formation at early stage in this model. Symbiofilm® has no bacteriostatic nor bactericidal activities.
 
To date, properly designed study to evaluate the effect of topical therapies on microbiome are scarce so no definite conclusion can be made. In one study, use of saline irrigation with or without budesonide^{DCI} used was not associated with significantly distinct microbiota composition among either controls or post-operative CRS with polyp patients [10].
 
We design this exploratory study aiming at determining if the antibiofilm properties of Symbiofilm® may modify sino-nasal microbiota, impacting α and/ or β diversities. To this end middle meatus swab specimen will be taken from CRS patients before and after treatment with Healsea® Chronic. Bacteria colonization will be assessed using quantitative PCR and 16S rRNA gene sequencing.

--	--

Objectives:	
Primary Objective:
 
 - To characterize the change of sino-nasal microbial communities from adult CRS patients via 16S rRNA gene high throughput sequencing before and after 1-month treatment duration with Healsea® Chronic. 
Secondary objectives:
 
 -To assess the efficacy of Healsea® Chronic in improving health-related quality of life of CRS adult patients. -To assess the global satisfaction of patients with the use of Healsea® Chronic for CRS. - Safety: to assess systemic and local tolerance of Healsea® Chronic over the study period.
Endpoints:	
Primary endpoint:
 
Modifications in microbial load and/or profile
 
To determine the impact of Healsea® Chronic on the nasal microbiome, the microbial load will be evaluated by quantitative PCR and microbiome taxonomic profiling by 16S rRNA gene sequencing. Data collected in patients before and after 1 month-treatment with Healsea® Chronic will be compared using statistical analyses to assess changes in microbial species abundance and diversity. Furthermore, special attention will be given to typical sino-nasal pathogens (e.g. Staphylococcus aureus, Streptococcus pneumoniae, Haemophilus influenzae, Moraxella catarrhalis) at genus level, and if reachable at species level.
 
Secondary Endpoints:
 
 -To measure the clinical performance of Healsea® Chronic, the quality of life of CRS patients will be assessed with the Sino-Nasal Outcome Test score-22 (SNOT-22) [11]. This questionnaire is a disease-specific, quality-of-life-related measure of sinonasal function. Patients should rate sino-nasal symptoms and their impact from 0 to 5 where 0 means that there is no complaint and 5 means that there are serious complaints. - Patient satisfaction questionnaire assessing medical device usability, sensory perception and efficacy in using Healsea® Chronic for CRS. - Safety: Assessment of adverse events/incidents/expected side effects throughout the study.
Indication:	Treatment of nasal symptoms of chronic rhinosinusitis
Investigation Design:	
PMCF investigation for MD CE marked and used in its intended purpose with invasive and/or burdensome procedure (MDR Art. 74(1)).
 
Non randomized, open and uncontrolled interventional study.

	
Visit 1 (V1) – (Day 1): Screening/Inclusion Information and consent, demographic data and medical history, ongoing medication, rhinologic examination, inclusion/non-inclusion criteria, collection of middle meatus swab specimens, SNOT-22, reporting of adverse events, dispensation of Healsea® Chronic Nasal Spray.
 
Telephone call 1 (TC1) – (Day 15±3) Investigator/nurse telephone call to review patient status and study progress, adverse events/incidents/expected undesirable side effects and concomitant treatments.
 
Visit 2 (V2) – (Day 30±5): end of treatment End of Healsea® Chronic nasal spray treatment, physical and clinical examination, reporting of adverse events/incidents/expected side effects, collection of middle meatus swab specimens, SNOT-22, subject's satisfaction questionnaire.

Number of Subjects:	An arbitrary sample of 20 subjects
Target Population:	Adults with chronic rhinosinusitis according to EPOS criteria [1].
Permitted and prohibited concomitant medication	
Permitted concomitant medication: Nasal corticosteroids
 
Not permitted concomitant medication: Other nasal irrigations Need for systemic corticosteroids Need for nasal application of antibiotics and systemic antibiotics

Inclusion/Non inclusion criteria:	
Inclusion criteria In order to be eligible to participate in this study, an individual must meet all of the following criteria:
 
 1. Male or female, aged 18 – 70 years 2. Provision of signed and dated informed consent form 3. Stated willingness to comply with all study procedures and availability for the duration of the study 4. Diagnosed with CRS based on the diagnostic criteria of the EPOS guideline 5. Registered with a social security scheme or covered by such a regime 
Non inclusion criteria An individual who meets any of the following criteria will be excluded from participation in this study:
 
 1. Antibiotics or oral corticosteroids intake in the month prior to the study 2. Endoscopic sinus surgery in the past 6 months 3. Cystic fibrosis 4. Wegener's granulomatosis 5. Immunodeficiency

	
 6. Defective access to middle meatus 7. Lidocaine allergy 8. Known hypersensitivity/allergy to any component of the test device 9. Pregnant/Lactating female or absence of efficient contraception 10. Under tutorship or guardianship
Number of sites:	1
Test Device:	Healsea® Chronic nasal spray will be administered twice a day (1 puff, 1-2 sec) in each nostril during 30 days.
Comparator Device:	Not applicable
Duration of investigation:	
Duration of inclusion period: 4 months
 
Duration of patient's participation: 30 days
 
Total study duration: 5 months

Study Start Date:	September 2021
Statistical Analysis:	
Patients and disease characteristics will be described at baseline.
 
16S rRNA Gene Sequence Analysis: The normal distribution of the values is verified thanks to normality tests (e.g. Shapiro-Wilk test). However, it is most likely that the group size will be insufficient to apply parametric statistical tests. Significant variations in total number of bacterial 16S rRNA gene copies or in alpha diversity are assessed using the Kruskal-Wallis test or the Wilcoxon rank-sum test. Multidimensional scaling analyses (MDS) are performed on beta diversity distances matrices and differences between groups were assessed using PERMANOVA and PERMDISP analyses (2000 permutations). LEfSe (Linear discriminant analysis Effect Size) analyses, based on non-parametric tests are used to determine significant variations in taxa relative abundance [17].
 
Secondary endpoints: Values and changes from baseline to D30/end of study of the SNOT-22 total score will be described. Patients satisfaction will be described at D30/end of study.
 
Safety: All adverse events/incidents/expected side effects of the device will be listed, but only treatment-emergent adverse events/incidents (non-serious + serious) and expected side effects will be summarized by the number and percentage of patients, classified by System Organ Class and Preferred Term as defined by MedDRA dictionary. Frequency and percentage of patients with at least one reported adverse event/incident/expected side effect will be tabulated by System Organ Class.

3. Flow Chart

Visit name	Screening/Inclusion	At home	Telephone call	At home	End of Treatment
Visit Number	V1		TC1		V2
Days/Weeks	D1	D1 – D15± 3	D15±3	D15± 3 – D30± 5	D30 ± 5
Screening and General Assessments					
Patient information and Consent collection	X				
Eligibility criteria	X				
Demography and Medical history	X				
Physical and clinical examination	X				X
Ongoing medication	X				
Treatment					
Healsea® Chronic		X		X	
Assessments					
SNOT 22	X				X
Collection of middle meatus swab specimens	X				X
Adverse Events/incidents and concomitant medication reporting	X		X		X
Satisfaction questionnaire					X
Compliance to study product					X

4. Identification and description of the investigational Device

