7.2 Primary Objective

To characterize the change of sino-nasal microbial communities from adult CRS patients via 16S rRNA gene high throughput sequencing before and after 1-month treatment duration with Healsea® Chronic.

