7.3 Secondary Objectives

- To assess the efficacy of Healsea® Chronic in improving health-related quality of life of CRS adult patients.
- To assess the global satisfaction of patients in using Healsea® Chronic nasal spray for CRS.
- Safety: to assess systemic and local tolerance of Healsea® Chronic over the study period.

7.4 Scientific justification and clinical relevance for effect sizes, non inferiority margins or equivalence

Not applicable. This is an exploratory clinical investigation.

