8.3.6 Number of subjects required to be included in the clinical investigation

An arbitrary sample of 20 patients completing the investigation without major protocol deviation has been chosen.

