8.5.2 Monitoring

Study monitoring under responsibility of Lallemand Pharma by qualified staff will be performed at various stages of the study. Monitoring will include on-site visits and centralized data review to assure that the investigation is conducted according to the CIP and comply with applicable regulations and deadlines. On-site review of Case Report Form (paper CRFs) will include the review of forms for completeness, clarity and consistency with source documents available for each subject. In case of queries, the investigator should respond within agreed timelines.

The investigator must permit study-related monitoring visits, audits review by the Ethic Committee and ANSM, and allow direct access to source data and source documents provided that subject confidentiality is protected. In case of an audit appointed by Lallemand Pharma, the investigator will receive written notification in advance.

9. Statistical design and analysis

Patients and disease characteristics will be described at baseline.

16S rRNA Gene Sequence Analysis

The normal distribution of the values is verified thanks to normality tests (e.g. Shapiro-Wilk test). However, it is most likely that the group size will be insufficient to apply parametric statistical tests. Significant variations in total number of bacterial 16S rRNA gene copies or in alpha diversity are assessed using the Kruskal-Wallis test or the Wilcoxon rank-sum test. Multidimensional scaling analyses (MDS) are performed on beta diversity distances matrices and differences between groups were assessed using PERMANOVA and PERMDISP analyses (2000 permutations). LEfSe (Linear discriminant analysis Effect Size) analyses, based on non-parametric tests are used to determine significant variations in taxa relative abundance [17].

Secondary endpoints

Values and changes from baseline to D30/end of study of the SNOT-22 total score will be described.

Patients satisfaction will be described at D30/end of study.

Safety

All adverse events/incidents/expected side effects will be listed, but only treatment-emergent adverse events/incidents (non-serious + serious) and expected side effects will be summarized by the number and percentage of patients, classified by System Organ Class and Preferred Term as defined by MedDRA dictionary.

Frequency and percentage of patients with at least one reported adverse event/incident/expected side effect will be tabulated by System Organ Class.

10. Data collection

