4. SAMPLE SIZE

An arbitrary sample of 20 subjects completing the investigation without major protocol deviation has been chosen.

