6.3. Statistical/Analytical issues

6.3.1. Significance level

All statistical analyses will be performed at the 0.05 global significance level (type I error rate), using two-sided tests.

Because of the exploratory nature of the study, all the statistical results have to be considered within a descriptive perspective and not as inferential issues. No adjustment for Type I error is done. P-values of statistical tests will be provided for information only.

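### For microbial load and alpha diversity the protocol names only significance tests; neither document plans an estimate, with interval, of the within-patient change

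*Protocol*

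**What the plan says.** Protocol 7.2 states the aim of the primary analysis: "To characterize the change of sino-nasal microbial communities from adult CRS patients". The tool is 16S sequencing of swabs taken on either side of a month of treatment. Protocol 8.1.3 defines the endpoint as a modification in load and/or profile, with load measured by qPCR.

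The analysis is in Protocol section 9, repeated in the synopsis. It starts with a normality check, adds that "it is most likely that the group size will be insufficient to apply parametric statistical tests", and continues: "Significant variations in total number of bacterial 16S rRNA gene copies or in alpha diversity are assessed using" a Kruskal-Wallis or a Wilcoxon rank-sum test. Nothing further is said about load or alpha diversity. Beta diversity gets an MDS ordination followed by PERMANOVA and PERMDISP. Taxa get LEfSe.

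For SNOT-22, the same section 9 has both the values and the changes from baseline described. SAP 6.2 and 10.2 carry this through with mean, SD, median, quartiles and range.

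SAP 6.3.1 keeps a two-sided 0.05 level but says that "all the statistical results have to be considered within a descriptive perspective and not as inferential issues", and that p-values are informational. SAP sections 5 and 10.1 pass the primary criterion to a specialist microbiome team and a separate document, which is not among those supplied.

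On size, Protocol 8.3.6 says "An arbitrary sample of 20 patients completing the investigation without major protocol deviation has been chosen", and SAP section 4 says the same. On effect size, Protocol 7.4 says "Not applicable. This is an exploratory clinical investigation".

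**The concern.** An objective to characterise a change asks how large the change is, in which direction, and how precisely it is known. For load and alpha diversity the only output named is a p-value, which answers none of these. It is also the kind of output that SAP 6.3.1 gives least weight. The result is uneven: a secondary questionnaire score has its change described, while two components of the primary endpoint do not.

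Protocol 6.6 says that an observed improvement in the microbiota could justify further study in a larger population. Anyone weighing or sizing such a study would want the estimated change and its uncertainty. Because 20 is an arbitrary number with no target effect behind it, an interval is also the direct way to show what the data can and cannot exclude. Without one, a non-significant result may be taken as no change when the data are simply imprecise.

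**Working it through.** **Inputs from the documents.** 20 completers (Protocol 8.3.6, SAP 4); one V1 and one V2 swab each (Protocol 8.1.5.1); two-sided 0.05 (SAP 6.3.1); no replacement (Protocol 8.1.7). The documents give no SD, correlation, effect size, power or precision target, so there is no stated figure to reproduce.

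**Assumptions.** Normally distributed values. SD of the within-patient change in log10 copies between 0.3 and 1.0. Within-patient correlation between visits of 0.3 to 0.7.

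**Step 1: precision with 20 pairs.** The half-width of the 95% interval for a mean paired change, in units of the SD of the change, is t(0.975, n−1)/√n.
- n = 20: 2.093/4.472 = 0.468
- n = 18: 0.497
- n = 16: 0.533

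**Step 2: the same as a fold change in load (n = 20).** Half-width in log10 units = 0.468 × SD; fold = 10^(half-width).

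| Assumed SD of log10 change | Half-width (log10) | Multiply or divide by |
|---|---|---|
| 0.3 | 0.140 | 1.38 |
| 0.5 | 0.234 | 1.71 |
| 0.8 | 0.374 | 2.37 |
| 1.0 | 0.468 | 2.94 |

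At an SD of 0.5 to 1.0, an estimate of exactly no change would therefore be compatible with anything up to a 1.7- to 2.9-fold rise or fall.

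**Step 3: how often a test alone would miss a moderate change.** The table comes from 4,000 simulated studies of 20 pairs, with a true shift of 0.5 of the single-visit SD. In units of the SD of the change the shift is 0.5/√(2(1−ρ)), which is 0.42, 0.50 and 0.65 at correlations ρ of 0.3, 0.5 and 0.7.

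| ρ | Rank-sum power (named in the protocol) | Missed | Signed-rank power (paired, not named) | Missed |
|---|---|---|---|---|
| 0.3 | 30.2% | 69.8% | 41.7% | 58.3% |
| 0.5 | 26.5% | 73.5% | 54.2% | 45.8% |
| 0.7 | 23.9% | 76.1% | 75.7% | 24.3% |

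The rank-sum test treats the two samples from one patient as independent. With no true change, its rejection rate in the same simulations was 2.6%, 0.6% and 0.2% at the three correlations, against a nominal 5%. The signed-rank test stayed between 4.8% and 5.6%. So a p-value from the named test is a poor guide to absence of change, and a paired estimate also brings the pairing back into the analysis.

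**Step 4: is an estimate planned elsewhere?** SAP 6.2 lists descriptive statistics, but SAP 5 and 10.1 remove the primary criterion from that plan, and the table list in SAP 13.2 has no table for load or diversity. In the supplied documents, Protocol section 9 and its copy in the synopsis are the only specification.

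**The case against.** The strongest reply is that SAP 10.1 places the primary analysis in a separate document. That document may well contain medians, fold changes and intervals, so the absence of any planned estimate cannot be asserted. This stands: the point concerns what the two supplied documents specify.

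A reader might infer that the whole primary analysis consists of tests. It does not. MDS is descriptive, and LEfSe, as its name in section 9 says, carries an effect size for taxa. The gap is load and alpha diversity, plus an unstated R-squared for beta diversity.

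A reader might also infer that the normality check makes the method depend on the data. No parametric test is named, the text already expects non-parametric methods, and no decision rule is attached, so the check selects nothing.

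Finally, one might say that the study cannot characterise the change, or that a null result will be reported as no change. SAP 6.3.1 works against that by making results descriptive, and Protocol 7.1 expects only preliminary insight into mechanism. Nor does Protocol 6.6 make this study decide on a larger one; it says only that an improvement could justify it. What remains is that a descriptive stance needs a descriptive quantity, and none is specified for these two components. Low precision follows from the openly arbitrary sample of 20. An interval would show it, not cure it.

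**Conclusion.** The point holds for microbial load and alpha diversity: as supplied, the plan gives tests and no estimate or interval for the within-patient change, which fits neither the objective nor SAP 6.3.1. The half-width of 0.47 SD rests on 20 complete pairs and a t interval for a mean. The 1.7- to 2.9-fold range rests further on an assumed SD of 0.5 to 1.0 for the log10 change. The miss rate of about 73% for the rank-sum test rests on an assumed shift of half a single-visit SD and a within-patient correlation of 0.5. The lower figure of about 46% at that correlation belongs to a paired test the protocol does not name.

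The documents do not support saying that no part of the primary endpoint has an effect measure, that the study is unable to meet its objective, or that the normality check drives the choice of method. This is a cheap improvement to an exploratory study.

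**What to change.** In Protocol section 9, the synopsis and the separate microbiome analysis document, replace the wording on load and alpha diversity with text such as:

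> The within-patient change (V2 minus V1) in log10 16S copies, back-transformed to a fold change, and in each alpha-diversity index will be reported as the Hodges-Lehmann paired estimate with its 95% confidence interval. Any accompanying p-value will come from the matching Wilcoxon signed-rank test and is supportive only. For beta diversity, the PERMANOVA R-squared will be reported.

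Naming the estimator and its matching test together avoids paired intervals beside p-values that ignore the pairing. LEfSe can stay as it is for taxa. The normality check can be dropped as a minor tidy-up.

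The cost is a few sentences and a few lines of code on data already to be collected; visits, swabs and patient numbers do not change. The downside is that the intervals will show openly how imprecise 20 patients are.
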